## **6.5. Concomitant Therapy**

Any medication or vaccine (including over-the-counter or prescription medicines, vitamins, and/or herbal supplements) that the participant is receiving at the time of enrollment or receives during the study must be recorded in the CRF, along with any changes to dose.

The medical monitor should be contacted if there are any questions regarding concomitant or prior therapy.

Participants and their study partners will be instructed to consult the investigator or other appropriate study personnel at the site before initiation of any new medications or supplements and before changing dose of any current concomitant medications or supplements.

### **6.5.1. Standard of Care for Alzheimer's Disease**

To ensure standard of care for AD, use of approved symptomatic treatments for AD is permitted in this study. The section below provides additional guidance on managing concomitant medication use.

Use of approved or standard of care symptomatic treatments for AD is permitted during the study, provided that the dose has been unchanged for 30 days before Visit 602. Doses of these medications should remain constant when possible through the study. When medically indicated, initiation, increase, or discontinuation of symptomatic treatments for AD is permitted.

Nonmedication treatments for AD, such as behavioral management, are permitted but are subject to the same restrictions as medication treatment taken for AD.

### **6.5.2. Medications for Infusion Reactions**

If an infusion reaction occurs, medications managing the reaction may be administered at the discretion of the investigator, according to local practice guidelines. If the need for concomitant medication arises, inclusion or continuation of the participant may be at the discretion of the investigator after consultation with a Lilly medical monitor. Concomitant therapy administered to treat an infusion reaction or as premedication for infusions should be documented.

### **6.5.3. Excluded Medications**

Immunoglobulin G therapy (also known as gamma globulin or IV immunoglobulin [IVIG]) is not allowed during the study. Other disease-modifying therapeutic agents may also be excluded medications (see Section [7.2](#) for additional details).

## **6.6. Dose Modification**

The dosing goal is for the participant to be titrated to the target dose of 1400 mg.

For participants who develop ARIA during the titration period (that is, before the fourth infusion of study drug), the investigator may decide to

- temporarily suspend dosing as described in Section 7.1.1.1, then determine if the participant should remain on 700 mg either temporarily beyond the first 3 doses or throughout the remainder of the treatment period,
- continue the 700 mg dose either temporarily beyond the first 3 doses or throughout the remainder of the treatment period, or
- continue the dosing schedule as outlined in Section 4.1.

## **6.7. Intervention after the End of the Study**

Not applicable.

## 7. Discontinuation of Study Intervention and Participant Discontinuation/Withdrawal

### 7.1. Discontinuation of Study Intervention

IP may be discontinued for a participant for the following reasons (details given below):

- By request of the participant or participant's designee (for example, legal guardian)
- Clinical judgment
- A hepatic event or liver test abnormality
- C-SSRS results
- ARIA
- Systemic hypersensitivity reaction
- Severe noncompliance
- The participant requires an excluded therapeutic agent
- Placement of device incompatible with MRI

In rare instances, it may be necessary for a participant to permanently discontinue (definitive discontinuation) IP. If IP is definitively discontinued, the participant will remain in the study (following the SoA, except as noted below) to be evaluated for safety and efficacy.

If IP infusion is permanently discontinued and the participant remains in the study, 1 PK sample should be collected at the soonest scheduled visit regardless if PK collection is on the SoA at that visit. Dosing dates and times should be collected. Subsequent PK sample collection should follow the protocol SoA unless the scheduled visit exceeds 6 months since discontinuation of infusions. No additional PK collection is required once the participant exceeds 6 months since discontinuation of donanemab infusions.

#### Clinical Judgment

AE or clinically significant laboratory value, ECG result, physical examination finding, MRI finding (such as symptomatic ischemic stroke), C-SSRS result, or vital sign measurement of such severity that, in the opinion of the investigator or Lilly-designated medical monitor, continued treatment is not in the best interest of the participant.

#### Hepatic Event or Liver Test Abnormality

Participants who are discontinued from IP due to a hepatic event or liver test abnormality should have additional hepatic safety data collected via the CRF.

Discontinuation of the IP for abnormal liver tests **should be** considered by the investigator when a participant meets 1 of the following conditions after consultation with the sponsor-designated medical monitor:

- ALT or AST >8X ULN
- ALT or AST >5X ULN for more than 2 weeks
- ALT or AST >3X ULN and TBL >2X ULN or INR >1.5
- ALT or AST >3X ULN with the appearance of fatigue, nausea, vomiting, right upper-quadrant pain or tenderness, fever, rash, and/or eosinophilia (>5%)
- ALP >3X ULN

- ALP >2.5X ULN and TBL >2X ULN
- ALP >2.5X ULN with the appearance of fatigue, nausea, vomiting, right quadrant pain or tenderness, fever, rash, and/or eosinophilia (>5%)

#### C-SSRS

In addition, IP may be discontinued if participants:

- Answer “yes” to Question 4 or Question 5 on the “Suicidal Ideation” portion of the C-SSRS, or
- Answer “yes” to any of the suicide-related behaviors on the Suicidal Behavior portion of the C-SSRS.

A psychiatrist or appropriately trained professional may assist in the decision to discontinue the participant.

#### ECG

If a clinically significant finding is identified (including, but not limited to, changes from baseline in QT interval corrected using QTcF) after enrollment, the investigator or qualified designee will determine if the participant can continue in the study and if any change in participant management is needed. This review of the ECG printed at the time of collection must be documented. Any new clinically relevant finding should be reported as an AE.

#### ARIA

Treatment with IP may be permanently discontinued in participants with TE ARIA-E and/or ARIA-H at the discretion of the PI depending on severity of clinical and radiologic findings (see Manual of Operations for permanent discontinuation guidance). For temporary discontinuation for ARIA-related reasons, see Section 7.1.1.1.

#### Systemic Hypersensitivity Reaction

If the investigator, after consultation with the sponsor-designated medical monitor, determines that a systemic hypersensitivity reaction has occurred related to IP administration, the participant should be permanently discontinued from the investigational drug.

#### Severe Noncompliance

Severe noncompliance to the study protocol, that results in a safety concern, in the judgment of the investigator, may be reason for discontinuing IP.

#### Excluded Therapeutic Agent

The participant, for any reason, requires a treatment with an excluded therapeutic agent (Section 6.5.3) and temporary discontinuation criteria cannot be met (see Section 7.1.1.2).

#### Placement of Device Incompatible with MRI

Participants who require a ferromagnetic implant or insertion of a cardiac pacemaker that is not MRI-compatible will be permanently discontinued from IP and should have no MRIs. If the participant discontinues from the study, with the exception of an MRI, the participant should have end-of-therapy and/or end-of-study procedures performed as shown in the SoA.

### **7.1.1. Temporary Discontinuation**

#### **7.1.1.1. Due to ARIA**

The development of ARIA-E and/or ARIA-H (microhemorrhages and/or cortical superficial siderosis) are expected events for some participants due to the treatment with donanemab. The site PI may temporarily discontinue IP if the participant develops TE ARIA-H or ARIA-E to an extent deemed clinically significant by the site PI (see Manual of Operations for temporary discontinuation guidance). Reinitiating IP can be considered after resolution of ARIA-E and stabilization of ARIA-H imaging findings and the resolution of any associated symptoms. Both discontinuation and re-initiation decisions may be discussed with the sponsor. Dose modification considerations are described in Section 6.6.

In the event of a finding of ARIA-E on MRI, the investigator is to complete the CRF regarding the presence or absence of symptoms related to the ARIA-E.

In cases of new ARIA-E or ARIA-H, given the context of the severity of the imaging findings and symptoms, the site PI, at his/her clinical discretion, can elect to recommend discontinuing IP and then follow the participant with serial MRIs every 4 to 6 weeks (fluid attenuation inversion recovery [FLAIR] and T2\* gradient-recall echo) and monitor symptoms, to monitor stabilization or resolution. Upon resolution of ARIA-E and stabilization of ARIA-H and the resolution of any associated symptoms, the participant can be considered for re-initiating IP. There is no defined time duration for this monitoring period while off IP and will be based on clinical judgment. See the Manual of Operations for temporary and permanent discontinuation guidance.

#### **7.1.1.2. Due to Reasons Other than ARIA**

Temporary discontinuation from IP treatment is allowed if a short-term treatment with an excluded medication is necessary, secondary to hospitalization, personal circumstances or to evaluate the IP impact on an uncertain AE.

IP may be restarted at the next scheduled visit, at the investigator's discretion.

If temporary discontinuation is due to an AE, it should be reported to the Lilly medical monitor. Temporary treatment discontinuation and restarting should be documented. Restarting treatment after a discontinuation period that is greater than 12 weeks should be discussed between the investigator and Lilly medical monitor.

## **7.2. Participant Discontinuation/Withdrawal from the Study**

A participant may withdraw from the study:

- at any time at his/her own request
- at the request of his/her designee (for example, parents or legal guardian)
- at the discretion of the investigator for safety, behavioral, compliance, or administrative reasons
- if the participant becomes pregnant during the study
- if the participant enrolls in any other clinical study involving an investigational medicinal product or enrollment in any other type of medical research judged not to be scientifically or medically compatible with this study

- if the participant, for any reason, requires treatment with another disease-modifying therapeutic agent that has been demonstrated to be effective for treatment of the study indication, discontinuation from the study occurs prior to introduction of the new agent
- participation in the study needs to be stopped for medical, safety, regulatory, or other reasons consistent with applicable laws, regulations, and GCP
  - includes findings of exclusory MRI, hematology, or clinical chemistry at an unscheduled procedure prior to the participant starting Part B.

NOTE: If a clinically important abnormality, as determined by the investigator, in physical or neurological examination, vital sign, ECG, or clinical laboratory test results could be detrimental to the participant or could compromise the study, then the participant should not receive IP in Part B.

Participants must not enter Part B if the final centrally read MRI from the originating study or unscheduled MRI performed in Study AACH prior to Part B demonstrate presence of ARIA-E, >4 cerebral microhemorrhages, more than 1 area of superficial siderosis, any macrohemorrhage, severe white matter disease, significant abnormality that would suggest another potential etiology for progressive dementia, or a clinically significant finding that may impact the participant's ability to safely participate in the study.

At the time of discontinuing from the study, if possible, an early discontinuation visit should be conducted if participant completed Visit 1 and received IP (Part B only), as shown in the SoA. See SoA for data to be collected at the time of study discontinuation and follow-up and for any further evaluations that need to be completed. The participant will be permanently discontinued both from the IP and from the study at that time.

If the participant withdraws consent for disclosure of future information, the sponsor may retain and continue to use any data collected before such a withdrawal of consent. If a participant withdraws from the study, he/she may request destruction of any samples taken and not tested, and the investigator must document this in the site study records.

### **7.2.1. Discontinuation of Inadvertently Enrolled Participants**

If the sponsor or investigator identify a participant who did not meet enrollment criteria and was inadvertently enrolled, discussion should occur between the sponsor and investigator. If the investigator and the Lilly medical monitor agree it is medically appropriate to continue, the investigator must obtain documented approval from the Lilly medical monitor to allow the inadvertently enrolled participant to continue in the study with or without treatment with IP. Safety follow-up is as outlined in Section 1.3 (SoA), Section 8.2 (Safety Assessments), and Section 8.3 (AEs and SAEs) of the protocol.

### **7.3. Lost to Follow-Up**

A participant will be considered lost to follow-up if he or she repeatedly fails to return for scheduled visits and is unable to be contacted by the study site. Site personnel are expected to make diligent attempts to contact participants who fail to return for a scheduled visit or were otherwise unable to be followed up by the site.

Site personnel, or an independent third party, will attempt to collect the vital status of the participant within legal and ethical boundaries for all participants randomized, including those who did not get IP. Public sources may be searched for vital status information. If vital status is determined to be deceased, this will be documented, and the participant will not be considered lost to follow-up. Sponsor personnel will not be involved in any attempts to collect vital status information.

Discontinuation of specific sites or of the study as a whole are handled as part of regulatory, ethical, and trial oversight considerations in Section [10.1.8](#).

## **8. Study Assessments and Procedures**

Study procedures and their timing are summarized in the SoA. Protocol waivers or exemptions are not allowed.

Immediate safety concerns should be discussed with the sponsor immediately upon occurrence or awareness to determine if the participant should continue or discontinue IP.

Adherence to the study design requirements, including those specified in the SoA, is essential and required for study conduct.

All screening evaluations must be completed and reviewed to confirm that potential participants meet all eligibility criteria. The investigator will maintain a screening log to record details of all participants screened and to confirm eligibility or record reasons for screening failure, as applicable.

### **8.1. Efficacy Assessments**

#### **8.1.1. Cognitive and Functional Measures**

The following cognitive and functional measures will be included in this study:

- ADAS-Cog13
- ADCS-ADL
- MMSE
- CDR-SB

These measures are utilized in Parts A, B, and C. For differences in administration of the measures, see Section 8.1.2.

##### **8.1.1.1. CDR-SB**

The CDR-SB (Hughes et al. 1982; Morris 1993) is a global assessment tool that can be used to effectively evaluate both cognition and function. The tool was initially developed to measure dementia severity and covers 6 categories or “boxes”: Memory, Orientation, Judgment and Problem Solving, Community Affairs, Home and Hobbies, and Personal Care.

The CDR global ratings, calculated using an algorithm, range from 0 (no dementia) to 3 (severe dementia) while CDR-SB scores, calculated by adding the box scores, range from 0 to 18 (with higher scores indicative of more impairment). Scoring is determined by a clinician through a semistructured and in-depth interview with both the affected individual and their study partner. The study partner and participant must be interviewed separately.

This scale demonstrates acceptable psychometric characteristics (Coley et al. 2011; Cedarbaum et al. 2013) and has been shown to be sensitive enough to detect disease progression, even in populations with less advanced clinical disease (Williams et al. 2013; Wessels et al. 2015).

##### **8.1.1.2. MMSE**

The MMSE is a brief instrument used to assess cognitive function in patients (Folstein et al. 1975).

The instrument measures orientation, memory, and attention; the ability of the participant to name objects; follow verbal and written commands; write a sentence; and copy figures. The range for the total MMSE score is 0 to 30, with lower scores indicating greater level of impairment.

#### **8.1.1.3. ADAS-Cog13**

The ADAS-Cog13 is a rater-administered instrument that was designed to assess the severity of dysfunction in the cognitive and noncognitive behaviors characteristic of persons with AD (Rosen et al. 1984).

The cognitive subscale of the ADAS, the ADAS-Cog13, consists of 13 items assessing areas of cognitive function that are the most typically impaired in AD: orientation, verbal memory, language, praxis, delayed free recall, digit cancellation, and maze-completion measures (Mohs et al. 1997). The ADAS-Cog13 scale ranges from 0 to 85, with higher scores indicating greater disease severity.

#### **8.1.1.4. iADRS**

The iADRS (Wessels et al. 2015) represents a composite that was developed using both a theory-driven approach (incorporating measures of both cognition and function) and a data-mining approach (identifying the most sensitive combination of scales through analysis of data from the AD Neuroimaging Initiative and the EXPEDITION, EXPEDITION2, and EXPEDITION3 studies).

The iADRS is a simple linear combination of scores from 2 well-established, therapeutically sensitive, widely accepted measures in AD, the ADAS-Cog13 and the ADCS-iADL, measuring the core domains of AD. All items of these 2 scales are included without additional weighting of items, yielding face validity and ease of interpretation of the composite relative to its components.

The iADRS score will be derived from the ADAS-Cog13 and the ADCS-iADL. The ADAS-Cog13 and the ADCS-ADL will be the actual scales administered to participants.

#### **8.1.1.5. ADCS-ADL**

The ADCS-ADL is a 23-item inventory developed as a rater-administered questionnaire that is to be answered by the participants study partner (Galasko et al. 1997, 2004).

For each of the specific items, the study partner is first asked if the participant attempted the ADL during the past 4 weeks. If the participant did attempt the ADL, the study partner is asked to rate the performance level based on a set of performance descriptions. Scores for each item and the overall score for the tool are calculated. The range for the total ADCS-ADL score is 0 to 78, with lower scores indicating greater level of impairment (Galasko et al. 1997, 2004).

### **8.1.2. Order of Assessments and Rater Roles**

Assessments administered to the participant are the MMSE, ADAS-Cog13, CDR, and C-SSRS (C-SSRS is in Part B only). Assessments administered to the study partner are the CDR and ADCS-ADL.

Refer to the table below for the sequence of tests for both participant and study partner.

Psychometric Rater	Global Rater
Participant	Study Partner
1: MMSE	1: ADCS-ADL
2: ADAS-Cog 13	2: CDR a
	Participant
4: C-SSRS (Part B only)	3: CDR a

Abbreviations: ADAS-Cog13 = Alzheimer's Disease Assessment Scale – Cognitive subscale;

ADCS-ADL = Alzheimer's Disease Cooperative Study – Activities of Daily Living Inventory; CDR = Clinical Dementia Rating Scale; C-SSRS = Columbia Suicide Severity Rating Scale; MMSE = Mini Mental State Examination; VTC = video teleconference.

a The CDR must always be administered to the study partner first and then to the participant. It is recommended that both sections are administered on the same day. For VTC assessment, the participant and the study partner cannot be present during the other party's interview.

Note that, in Parts B and C, the ADAS-Cog13 and MMSE should be administered by a different rater than the ADCS-ADL and CDR.

In Part A, for Pair 1 within each subject, the VTC assessment and the on-site assessment must be conducted by 2 separate raters. In subsequent pairs, every effort should be made to have separate raters conduct the VTC assessment and the on-site assessment.

In Part B, the global and psychometric raters should administer the same scale to the same participant throughout the study whenever possible. The PI has the responsibility of selecting the raters who will administer the instruments at the site, and ensuring all training requirements have been met by those raters.

When administered, cognitive and functional testing should be performed before medical procedures that could be stressful for the participant (e.g., blood draws). Note that some procedures (MRI, floratacupir F 18 PET tau imaging, florbetapir F 18 PET amyloid imaging) can be conducted on other days within the visit window. The CDR rater should be blinded to AEs to avoid bias in the CDR assessment.

Cognitive and functional testing will be administered using an eCOA tablet. The audio voice recordings of the rater's questions and the participant's and study partner's responses will also be collected via the eCOA tablet during administration of the cognitive and functional testing for central monitoring of rater scale administration. Cognitive and functional testing for each participant should be performed at approximately the same time on each day, whenever possible, to reduce potential variability.

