## Part C

	Part C	Comments
Visit Number	201	
Timing	Any time $\geq$ 52 weeks after participant's last double-blind visit in the originating study.	Procedures may take more than 1 day.
PET Scans		
Flortaucipir F 18 PET scan	X g	
Florbetapir F 18 PET scan	X g	
Clinician Administered Assessments (Electronic)		
ADAS-Cog 13	X	If a PET scan is done on the same day, administer the ADAS-Cog 13 , ADCS-ADL, CDR-SB, and MMSE prior to PET scan. These tests include the audio voice recording of the rater's questions and the participant and study partner responses to assessment questions.
ADCS-ADL	X	
CDR-SB (Global Sum of Boxes - CDR)	X	
MMSE	X	
P-tau	X	
NfL	X	
A $\beta$	X	
Exploratory biomarker samples	X	Collect unless not allowed or unfeasible due to local regulations.
AEs	X	
Concomitant medications	X	

Abbreviations: A $\beta$  = amyloid beta; ADA = antidrug antibody; ADAS-Cog13 = Alzheimer's Disease Assessment Scale – Cognitive subscale; ADCS-ADL = Alzheimer's Disease Cooperative Study – Activities of Daily Living Inventory; AE = adverse event; BP = blood pressure; CDR-SB = Clinical Dementia Rating Scale – Sum of Boxes; C-SSRS = Columbia Suicide Severity Rating Scale; CRF = case report form; ECG = electrocardiogram; ED = early discontinuation; IP = investigational product; IV = intravenous; IWRS = interactive web-response system; MMSE = Mini Mental State Examination; MRI = magnetic resonance imaging; NfL = neurofilament light chain; PET = positron emission tomography; PK = pharmacokinetics; P-tau = phosphorylated tau; UP = unscheduled procedure; UV = unscheduled visit; V = visit.

- a V601 occurs up to 30 days prior to V602. V602 cannot occur <30 days from the participant's last double-blind visit of the originating study. V602 through V607 each occur 4 weeks apart. Part A visits may occur up to 24 weeks prior to Part B (V1), for eligible participants. The exact week relative to V1 depends on the number of PAIRs in which the participant elects to participate. The time between the final visit of Part A and the first visit of Part B or Part C is  $\geq$ 4 weeks.
- b UP takes place at the start of Part B (prior to V1), and is only conducted if: participant's last MRI from the originating study is >12 months from V1, or last labs from the originating study were collected >6 months from V1. The investigator confirms continued eligibility as described in Section [7.2](#).

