#### **4.1.2. Part A: Video Assessment**

Part A is a multicenter, randomized, multiple crossover study to validate remote assessment of cognitive and functional scales. Part A begins at Visit 601 (randomization), after screening is complete. Participants are randomized to one of 2 groups, as described in the Schema and Overall Design (Sections 1.2 and 4.1, respectively) to be assessed both remotely (through VTC) as well as on-site.

Part A consists of 6 assessments or 3 pairs:

- Pair 1 comprises Visits 602 and 603
- Pair 2 comprises Visits 604 and 605
- Pair 3 comprises Visits 606 and 607

In each pair, each participant is assessed once remotely through VTC and once in person on-site. The participant may elect to proceed to Part B (Visit 1) at any time after participating in Part A Pair 1.

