## **6.3. Measures to Minimize Bias: Randomization and Blinding**

### **Part A**

For the video assessment period, participants will be randomized 1:1 to either

- Group 1: Cognitive/functional scale assessment performed on-site, followed by at-home (VTC) assessment, or
- Group 2: Cognitive/functional scale assessment at home (VTC), followed by on-site assessment.

To minimize bias, participants follow a crossover design, alternating between assessment locations, starting with their randomized initial location.

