6.5. Primary Objective

The primary objective of Part A of this study is to evaluate the reliability of VTC compared with on-site administered cognitive and functional measures. This will be assessed by estimating the intra-class correlation (ICC) and the associated 95% confidence interval for the first pair of

observations from participants and comparing the lower bound of the confidence interval to 0.70, the ICC cut-off for acceptable reliability.

Using the guidelines and notation for defining ICCs published by McGraw and Wong (1996), the ICC of primary interest for this study is a 2-way mixed model, interaction absent, with single measurements from each modality on participants, looking at absolute agreement – ICC(A,1). In the present study, the ‘raters’ are the two modalities by which the clinical scales are assessed, on-site and VTC. As we are interested in comparing these specific modalities, modality is considered a fixed effect.

For ADAS-Cog₁₃ total score, ADCS-ADL total score, iADRS total score, CDR Sum of Boxes, and MMSE total score, individual mixed models will be fit to the data with fixed effects of modality, time effect, age, years of education, and presence/absence of anti-dementia drugs and a random effect for subject. ICCs will be estimated using the mean squares from these models and defined as:

Absolute Agreement: $ICC (A,1) = (MS_{subj} - MS_{error}) / (MS_{subj} + MS_{error} + 1/n(MS_{modality} - MS_{error}))$

Consistency: $ICC (C,1) = (MS_{subj} - MS_{error}) / (MS_{subj} + MS_{error})$

95% Confidence intervals for these quantities will be constructed as specified in Table 7 of McGraw and Wong (1996).

Similar analyses will also be conducted for pairs 2 and 3 of each of the clinical outcomes specified above. As the number of subjects contributing additional pairs may be limited, no specific hypothesis/test is specified.

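### A failed Part A reliability result cannot be attributed to video, because each Pair 1 modality has a different rater 4 weeks apart, raters are not balanced over modality, and the ICC model has no rater term

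*Protocol*

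**What the plan says.** Part A compares video (VTC) with on-site scoring of four scales. The primary endpoint uses Pair 1 only. Four features matter here.

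- **Content of a pair.** Protocol 4.1.2: "In each pair, each participant is assessed once remotely through VTC and once in person on-site". No pair holds two assessments of the same modality.
- **Raters.** Protocol 8.1.2: "for Pair 1 within each subject, the VTC assessment and the on-site assessment must be conducted by 2 separate raters". For later pairs the rule softens: "every effort should be made to have separate raters conduct the VTC assessment and the on-site assessment". The same section adds that "The PI has the responsibility of selecting the raters who will administer the instruments at the site"; this sentence stands in the paragraph on Part B but is worded generally. Neither document rotates raters or balances them over modality.
- **Timing and order.** Footnote a of the Schedule of Activities: "V602 through V607 each occur 4 weeks apart", with a tolerance of ±4 days. Only the order of modality is randomized. Protocol 6.3: "participants follow a crossover design, alternating between assessment locations, starting with their randomized initial location".
- **Model.** SAP 6.5 treats the two modalities as the raters of the ICC: "As we are interested in comparing these specific modalities, modality is considered a fixed effect". The other terms are time, age, years of education, anti-dementia drug use and a random subject effect. There is no human-rater or site term.

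Success means that the lower 95% confidence limit of ICC(A,1) exceeds 0.70. The consistency version, ICC(C,1), is planned as a sensitivity analysis (Protocol 9.4.4). No same-modality ICC is planned.

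**The concern.** The two scores in a Pair 1 comparison differ in modality, in the person scoring, and by 4 weeks. All three sources lower the one ICC that is estimated. For ADCS-ADL the two recall periods are also largely different, because "the study partner is first asked if the participant attempted the ADL during the past 4 weeks".

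If the lower limit misses 0.70, the natural reading is that video is not acceptable. Two on-site assessments by two raters 4 weeks apart might do no better, and the planned analyses cannot show whether they would. At any site where one rater takes all the video sessions and the other all the on-site sessions, rater severity and modality cannot be separated at all. The documents neither require nor prevent this. Part A exists to validate remote assessment, so an uninterpretable failure would defeat its purpose.

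**Working it through.** **1. Inputs.** From Protocol 9.2: about 180 Pair 1 completers, correlation 0.80, equal means, SDs 8 and 9 on ADAS-Cog13, lower limit to exceed 0.70, stated power about 81%, stated mean ICC 0.793 (0.732 to 0.841). Not in the documents, so assumed: the two-rater 4-week reliability R without any video effect, the between-rater SD, and the number of raters and participants per site.

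**2. The plan's own figure.** The population ICC is 2 × 0.80 × 8 × 9 / (8² + 9²) = 115.2/145 = 0.794. Simulating normal pairs at n = 180 with the McGraw-Wong interval (200,000 runs) gives mean ICC 0.793, mean interval 0.732 to 0.841 and power 82.8%. That agrees with the stated 81% within the error of a 1000-iteration run (1.5 Monte Carlo standard errors). The power calculation is sound on its assumptions.

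**3. No video effect, varying R.** If video adds no error, the video/on-site correlation equals R.

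| R | Chance of passing, SD 8 and 9 | Chance of passing, both SDs 8.5 |
|---|---|---|
| 0.80 | 83% | 87% |
| 0.78 | 59% | 66% |
| 0.76 | 34% | 40% |
| 0.75 | 23% | 29% |

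With SDs 8 and 9 the chance reaches 50% at R of about 0.77. Below that, a perfectly equivalent video assessment would fail more often than not.

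**4. The reverse reading.** If the observed correlation is R × q, with q the part retained under video, then q = 0.80/R. An observed 0.80 fits R = 0.80 with no loss, R = 0.85 with 0.80/0.85 = 0.94 (6% loss), R = 0.90 with 0.89 (11%), or R = 0.95 with 0.84 (16%). Pair 1 data cannot choose among these.

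**5. Adding rater variance to 0.80.** Take SD 8.5 in both modalities: total variance 72.25, subject variance 0.80 × 72.25 = 57.8. A between-rater SD of s gives an ICC of 57.8/(72.25 + s²). The chances come from simulation with 30 sites of 6, two raters per site and no video effect.

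| Rater SD | 57.8/(72.25 + s²) | Chance of passing |
|---|---|---|
| 0 | 0.80 | about 87% |
| 1 | 57.8/73.25 = 0.79 | about 78% |
| 1.5 | 57.8/74.5 = 0.78 | about 61% |
| 2 | 57.8/76.25 = 0.76 | about 40% |

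Repeat runs differ by 1 to 3 points.

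**6. Does ICC(C,1) expose this?** No. At rater SD 2, ICC(A,1) is 0.755 and ICC(C,1) 0.757: rater differences that vary by site enter the error term of both. By contrast, a uniform shift of 2 points between modalities (SD 8 and 9) lowers ICC(A,1) to 0.77 and leaves ICC(C,1) at 0.79, so that source is visible.

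**7. What rotation does.** At rater SD 2, alternating raters over modality across participants leaves the unadjusted ICC at 0.76 and the chance of passing at about 40%. With rotation, however, the rater difference within a site can be estimated and removed. The rater-adjusted ICC returns to about 0.80 and the chance to 86–88%.

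**8. A trap in the same-modality benchmark.** Alternation already yields same-modality repeats 8 weeks apart (V602/V604, V603/V605) in participants who stay for Pair 2. If each rater stays with one modality within a participant, these repeats share a rater while the cross-modality pair does not. At rater SD 2 with no video effect, the same-modality ICC is then 0.81 against 0.76 cross-modality, a pure artefact. Swapping the two raters between pairs gives 0.755 for both.

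**The case against.** The strongest reply is that the two-rater rule is a sensible conservative choice: it stops one person's memory of earlier answers from inflating agreement. That stands, and the rule should stay. Randomized order, the time term, ICC(C,1), the longitudinal model comparing modalities at each visit (SAP 6.6), audio monitoring and rater training also deal with average shifts, time trends and rater quality. They do not estimate random or site-specific rater disagreement.

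It is also fair that the assumed 0.80 is a video/on-site correlation under this very design, so it may already contain rater and retest variation. Step 5 of the working would then count rater variance twice. The rater SDs, the site layout and the lower values of R have no source in the documents.

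Three stronger readings are tempting and not supported:

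- That the estimate has no comparator. On-site scoring is the comparator; what is missing is a measure of how well on-site scoring agrees with itself under the same two-rater, 4-week conditions.
- That the ADCS-ADL recall periods never overlap. The ±4-day tolerance allows visits less than 28 days apart, so some overlap is possible.
- That rotating raters would by itself recover the lost power. It does not.

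Finally, Pairs 2 and 3 are elective, and the protocol itself provides for fewer than 50 pairs. At 50 participants and an ICC of 0.80, the 95% half-width for a difference between ICCs is about 0.10 (about 0.07 at 100). Such a benchmark could not explain a narrow miss.

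**Conclusion.** The point holds as a limit on interpretation, in one direction. Independent rater and retest noise can only lower agreement, so a lower limit above 0.70 remains good evidence for video. A lower limit below 0.70 would not show that video is the cause, and no planned analysis would resolve the question.

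A reader might infer that video is likely to fail, or that the power calculation is wrong. Neither follows. The 81% reproduces, and the documents give no rater or retest reliability from which to judge how likely such a failure is. The fall from about 87% to 78%, 61% or 40% illustrates rater SDs of 1, 1.5 and 2 points. It rests on 30 sites of 6, SD 8.5 in both modalities, and rater variance added to 0.80 rather than already contained in it.

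The change is worth making because it is cheap and lets Part A answer its own question if the result is unfavourable.

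**What to change.** 1. **Protocol 8.1.2.** Keep two separate raters in Pair 1. Have each site alternate which rater takes video across successive participants, and swap the two raters between pairs within a participant where feasible. Make the rater ID available for analysis.
2. **SAP 6.5.** Leave the primary ICC unchanged. Add a sensitivity ICC adjusted for human rater, with the rater term and the error degrees of freedom specified in advance. State that a miss of 0.70 will be interpreted with this result beside it.
3. **SAP 6.5, descriptive.** In participants with two or more pairs, report same-modality and cross-modality ICCs with intervals, comparing only different-rater pairs with different-rater pairs. Note the 8-week against 4-week gap and the elective, possibly small subset.

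The cost is a sentence or two in 8.1.2 and the rater instructions, use of the rater ID, and extra SAP output. No raters or visits are added. Both raters at a site must be trained in both modes, a site with a single Part A participant contributes little to separating rater from modality, and the benchmark will be imprecise.
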